13.2. Sample Size, Accrual Rate and Study Duration

A total of 20 evaluable participants will be accrued within one year (up to 10 participants per cohort). Up to an additional 12 months of follow-up will be required on the last participant accrued to observe the participant's response to protocol therapy, for a total study duration of 2 years. There are no defined ethnic or racial accrual targets.

13.3. Stratification Factors

N/A

13.4. Interim Monitoring Plan

All participants will undergo continuous safety monitoring.

13.5. Analysis of Primary Endpoints

See Section 13.1

13.6. Analysis of Secondary Endpoints

See Section 13.1

13.7. Reporting and Exclusions

13.7.1. Evaluation of Toxicity

All participants will be evaluable for toxicity from the time of their first treatment.

13.7.2. Evaluation of the Primary Efficacy Endpoint

All participants in Cohort 1 who receive at least one dose of study treatment and all participants in Cohort 2 will be evaluable for response.

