1. OBJECTIVES

Study Hypothesis #1: Perampanel treatment reduces peritumoral hyperexcitability in newly diagnosed high grade glioma (HGG).

Study Hypothesis #2: Perampanel treatment in newly diagnosed HGG is associated with improvement in seizure control.

1 Study Design

This pilot study (Cohort 1) in participants with newly discovered radiologic lesions consistent with HGG evaluates the effect of perampanel on peritumoral hyperexcitability, measured by the rate of high frequency oscillations on intra-operative electrocorticography (ECoG), compared to a contemporary observational control group (Cohort 2) of participants undergoing ECoG and standard peri-operative seizure management. To estimate the effect size of early perampanel treatment on ongoing seizure control, participants in Cohort 1 will be maintained post-operatively on perampanel, adjusted on a clinical basis until evidence of disease progression (or maximum of 12 months), and compared to participants in Cohort 2 receiving standard of care post-operative seizure management.

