2. BACKGROUND

2.1 Study Disease(s)

This study evaluates peritumoral hyperexcitability and tumor-associated seizures in HGG, including WHO Grade III anaplastic astrocytoma and WHO Grade IV glioblastoma. Seizures are seen in up to 60% of patients with HGG,¹ and contribute to decreased quality of life.² While seizures generally occur earlier in the disease course, up to half of patients with HGG and

glioma-associated epilepsy continue to have uncontrolled seizures despite anti-seizure medications.^{3,4} To date, there are no evidence-based guidelines or widely accepted standards of care regarding the use and duration of anti-seizure medications to prevent seizures in this population, or evidence to guide the choice of one anti-seizure medication over another.⁵

Different glioma subtypes have unique propensities for the development of seizures, suggesting that gliomagenesis and epileptogenesis are inter-related, and that variable mechanisms may be involved.^{6,7} Among the mechanistic pathways with the most experimental evidence is dysregulation of glutamatergic signaling, whereby excitatory glutamatergic signaling pathways are upregulated in the glioma microenvironment, and contribute to excitotoxicity.^{7,8} Preclinical studies demonstrate an increase peritumoral glutamatergic hyperexcitability mediated through multiple mechanisms, including activation of the system x_c^- cystine-glutamate transporter, and AMPA-receptor mediated neuron-glioma synaptic activity.^{9,10} Recent evidence indicates that glioma growth is dependent on glutamatergic neuronal activity, mediated by the release of neuroligin-3 and the downstream activation of PI3K-mTOR signaling.^{8,11,12} Glutamate release from glioma cells leads to the development of neuronal-gliial synaptic connections, hyperexcitability, and further tumor growth in a positive feedback loop. Thus, excessive excitatory signaling appears to be a shared mechanism underlying tumor growth and epileptogenesis, and a promising therapeutic target.

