3. PARTICIPANT SELECTION

3.1 Eligibility Criteria

- 3.1.1 Participants must have radiologic evidence of anaplastic astrocytoma or glioblastoma multiforme within 14 days of enrollment.
- 3.1.2 Participants must have measurable disease, defined as at least one lesion that can be accurately measured in at least one dimension as ≥ 10 mm (≥ 1 cm) with CT or MRI. See Section 11 (Measurement of Effect) for the evaluation of measurable disease.
- 3.1.3 Age ≥ 18 years.
- 3.1.4 ECOG performance status ≤ 2 (Karnofsky $\geq 60\%$, see Appendix A).
- 3.1.5 Participants must have adequate organ and marrow function as defined below:
 - leukocytes $\geq 3,000/\text{mcL}$
 - absolute neutrophil count $\geq 1,500/\text{mcL}$
 - platelets $\geq 100,000/\text{mcL}$
 - total bilirubin \leq institutional upper limit of normal (ULN)
 - AST(SGOT)/ALT(SGPT) $\leq 3 \times$ institutional ULN
 - glomerular filtration rate (GFR) ≥ 30 mL/min/1.73 m² (see Appendix B)
- 3.1.6 Human immunodeficiency virus (HIV)-infected participants on effective anti-retroviral therapy with undetectable viral load within 6 months are eligible for this trial.
- 3.1.7 For participants with evidence of chronic hepatitis B virus (HBV) infection, the HBV viral load must be undetectable on suppressive therapy, if indicated.
- 3.1.8 Participants with a history of hepatitis C virus (HCV) infection must have been treated

and cured. For participants with HCV infection who are currently on treatment, they are eligible if they have an undetectable HCV viral load.

- 3.1.9 Participants with a prior or concurrent malignancy whose natural history or treatment does not have the potential to interfere with the safety or efficacy assessment of the investigational regimen are eligible for this trial.
- 3.1.10 Participants with known history or current symptoms of cardiac disease, or history of treatment with cardiotoxic agents, should have a clinical risk assessment of cardiac function using the New York Heart Association Functional Classification. To be eligible for this trial, participants should be class 2B or better.

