3.2 Exclusion Criteria

- 3.2.1 Participants with brain metastases due to confounding effects on the study objectives.
- 3.2.2 History of allergic reactions attributed to compounds of similar chemical or biologic composition to perampanel.
- 3.2.3 Participants receiving any medications or substances that are moderate or strong inducers of CYP3A4 are ineligible. Because the lists of these agents are constantly changing, it is important to regularly consult a frequently-updated medical reference. As part of the enrollment/informed consent procedures, the participant will be counseled on the risk of interactions with other agents, and what to do if new medications need to be prescribed or if the participant is considering a new over-the-counter medicine or herbal product.
- 3.2.4 Participants with uncontrolled intercurrent illness.
- 3.2.5 Participants with psychiatric illness/social situations that would limit compliance with study requirements.

- 3.2.6 Pregnant women are excluded from this study because perampanel is an anti-seizure agent with the potential for teratogenic or abortifacient effects. Because there is an unknown but potential risk for adverse events in nursing infants secondary to treatment of the mother with perampanel, breastfeeding should be discontinued if the mother is treated with perampanel.
- 3.2.7 Participants with a history of suicide attempt or current active suicidal ideation with intent as defined by Columbia Suicide Severity Rating Scale (C-SSRS) type 4-5, due to the potential for suicidal ideation with the use of all anti-seizure medications.
- 3.2.8 Participants who are unable to swallow pills.
- 3.2.9 Participants with tumor associated seizures greater than one month before planned surgery.
- 3.2.10 Participants currently receiving treatment with more than one anti-seizure medication.

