13.1. Study Design/Endpoints

Pilot Study: Preliminary Study

- Primary objective: Compare rates of peritumoral HFOs (mean number of HFOs per minute) between participants treated with perampanel versus standard of care.
- Secondary objective: Compare time to seizure recurrence between participants treated with perampanel versus standard of care up to the time of HGG progression.
- Maximum total accrual: 10 participants in Cohort 1, 10 participants in Cohort 2.
- Sample size justification: Using the mean HFO rate across participants receiving standard of care (Cohort 2) as the normalized ineffective rate ($P_1=1.0$), we define a target effective rate for the treatment arm (Cohort 1) of $P_2=0.60$. Using a two sample power calculation, the intended sample size of 10 participants in each cohort will provide 82.5% power to detect a true 40% or greater reduction in the normalized mean HFO rate with perampanel compared to standard of care ($\alpha=0.05$, two-sided).
- Statistical methods for primary objective: The primary endpoint is the mean number of HFOs per minute. This will be averaged across participants in each cohort, and compared using the Mann-Whitney U test (two-sided, $\alpha=0.05$). In sensitivity analyses, we will compare HFO rates between cohorts stratified by potential confounding variables, including temporal lobe tumor location, IDH1/2 mutation, and pre-operative seizures.
- Statistical methods for secondary objective: The secondary endpoint is the time to first post-operative seizure. Time to first post-operative seizure will be estimated in time-to-event analysis from the date of surgery using the Kaplan-Meier method. Comparison

between Cohort 1 and Cohort 2 will be performed using the log-rank test ($\alpha=0.05$). In sensitivity analyses, we will compare time to first post-operative seizure between cohorts stratified by potential confounding variables, including temporal lobe tumor location, extent of resection (gross total vs subtotal resection), presence of IDH1/2 mutation, and presence of pre-operative seizures.

- Data processing and statistical analysis will be performed using R 3.5.3 (The R Foundation for Statistical Computing).
- These results will be used to support or refute the hypothesis that perampanel has targeted anti-epileptogenic activity in glioma-associated epilepsy, and may inform the design and feasibility of future clinical studies of targeting the glutamatergic pathway in this patient population.

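### The primary analysis set has no pathology condition, so non-HGG participants stay in a 10-versus-10 comparison, and the accrual cap leaves no room for any participant without a usable ECoG

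*Combined protocol and SAP*

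**What the plan says.** Section 13.7.2 gives the rule for the primary efficacy endpoint. It counts Cohort 1 participants "who receive at least one dose of study treatment and all participants in Cohort 2 will be evaluable for response". It mentions neither histology nor an ECoG recording.

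Entry rests on imaging. Criterion 3.1.1 reads "Participants must have radiologic evidence of anaplastic astrocytoma or glioblastoma multiforme within 14 days of enrollment", and Section 1 describes the entrants as "participants with newly discovered radiologic lesions consistent with HGG". Sections 5.1 and 5.3.2 place the perampanel loading dose 12 to 36 hours before surgery, so Cohort 1 is dosed before tissue is available.

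The target disease is narrower. Both hypotheses in Section 1 are about newly diagnosed HGG, and Section 2.1 places the study "in HGG, including WHO Grade III anaplastic astrocytoma and WHO Grade IV glioblastoma". Criterion 3.2.1 excludes "Participants with brain metastases due to confounding effects on the study objectives".

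On numbers, Section 13.2 says "A total of 20 evaluable participants will be accrued within one year (up to 10 participants per cohort"), and Section 13.1 says "Maximum total accrual: 10 participants in Cohort 1, 10 participants in Cohort 2". Section 4 repeats the limit of 10 per cohort. Section 9.1 plans ECoG for everyone. No section gives a loss allowance, a replacement rule, or a rule for an unusable recording. The reasons for leaving therapy or study (5.5 and 5.7) do not include non-HGG pathology.

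**The concern.** The protocol itself treats one kind of non-HGG lesion as confounding, yet it has no rule for such a lesion when it is first identified at surgery. Followed literally, 13.7.2 keeps that participant in the primary comparison. The stratified sensitivity analyses in 13.1 cover tumor location, IDH1/2 mutation and pre-operative seizures, so they would not isolate the case either. Allocation follows participant preference or current cohort size (Section 4), so randomization does not balance non-HGG cases between cohorts.

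At stake is whether the primary result answers the HGG question. With 10 per cohort, one inclusion decision can change the estimate noticeably. If no rule is written beforehand, any departure from 13.7.2 would be decided after HFO rates are known.

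The second issue is the denominator. The primary endpoint exists only for a participant with a usable recording, and the cap equals the target.

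**Working it through.** **Inputs from the documents.** Normalized HFO rates 1.0 (control) and 0.60 (perampanel); 10 per cohort; two-sided alpha 0.05; stated power 82.5%; planned test Mann-Whitney (all 13.1). Cap 10 + 10 (Sections 4 and 13.1).

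**Not in the documents.** The SD of the HFO rate, the non-HGG fraction, the drug effect in non-HGG tissue, and the fraction of unusable recordings. Each is an assumption below.

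**Step 1: the stated 82.5%.** Without an SD, a two-means calculation cannot be reproduced. Treating 1.0 and 0.60 as proportions gives, two-sided, 62.5% (pooled), 73.3% (unpooled) or 86.5% (arcsine z). The stated figure appears if the arcsine effect size is entered as a standardized mean difference in a two-sided t test:

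- h = 2·asin(√1.0) − 2·asin(√0.60) = 1.369
- noncentrality = 1.369 × √(10×10/20) = 3.06, with 18 df, giving power 82.5%
- implied SD = 0.40 / 1.369 = 0.292

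A one-sided unpooled test of proportions also comes close (82.6%), but it contradicts the stated two-sided test. I use SD 0.292 because it is the value consistent with the plan's own figure under a two-sided t test.

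**Step 2: one non-HGG participant and the estimate.** Cohort means are 1.0 and 0.60 otherwise. The values 0.15 and 0.30 for a lesion with few HFOs are illustrative.

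| Case | Cohort means | Apparent reduction |
|---|---|---|
| None | 1.0 and 0.60 | 40% |
| One in Cohort 1, no drug effect, rate 1.0 | 1.0 and (9×0.60+1.0)/10 = 0.64 | 36% |
| One in Cohort 2, rate 0.30 | (9×1.0+0.30)/10 = 0.93 and 0.60 | 1 − 0.60/0.93 = 35% |
| One in Cohort 2, rate 0.15 | 0.915 and 0.60 | 34% |
| One in Cohort 1, rate 0.30 | 1.0 and (9×0.60+0.30)/10 = 0.57 | 43% |
| One in Cohort 1, rate 0.15 | 1.0 and 0.555 | 44% |

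The shift goes in either direction.

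**Step 3: power under the planned test.** Exact Mann-Whitney, simulated with normal rates and SD 0.292; values rounded.

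| Analysis set | Power |
|---|---|
| 10 and 10, all HGG | 79% |
| 9 and 9 | 72% |
| 8 and 8 | 70% |
| Keep 1 of 10 non-HGG per cohort, no drug effect | 67% |
| Keep 1 of 10, half the effect | 73% |
| Keep 2 of 10, no drug effect | 53% |
| Keep 2 of 10, half the effect | 68% |

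The rows to compare are 67% or 73% kept against 72% excluded (one per cohort), and 53% or 68% kept against 70% excluded (two per cohort).

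**Step 4: the cap.** If a usable participant means confirmed HGG with a usable recording, and losses are independent, the chance that all 20 are usable is (1 − d)^20. This is 0.95^20 = 36% at an assumed 5% loss and 0.90^20 = 12% at 10%. Keeping 10 usable per cohort would need 10/0.95 = 10.5, so 11 enrolled, or 10/0.90 = 11.1, so 12 enrolled. Both exceed the cap. By the t test of Step 1, one loss (9 and 10) lowers 82.5% to 80.2%, and one per cohort (9 and 9) lowers it to 77.8%.

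**The case against.** The strongest reply is that this is a self-described pilot in people with lesions that look like HGG on imaging. Analysing the population as it is recruited is a defensible pragmatic choice, and every power figure above rests on a back-solved SD. The point about the SD stands in full. The pragmatic argument stands only in part: the hypotheses, the background and criterion 3.2.1 all frame the question as one about HGG. Nor does 3.2.1 settle the matter, since it names only metastases and no section says that a participant found to have one after surgery leaves the analysis.

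A reader might infer that participants without an ECoG also dilute the comparison. They cannot, because they have no HFO rate to enter into the test.

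A reader might also infer that 20 evaluable participants cannot be delivered under a cap of 20. The documents do not support that. Read literally, 13.7.2 counts almost everyone, so 20 enrolled with all of Cohort 1 dosed gives 20 evaluable. What is missing is any slack, both for a Cohort 1 participant who is registered but never dosed and for anyone without a usable recording.

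Finally, excluding non-HGG cases does not reliably raise power. The gain disappears if such tissue shows half the drug effect.

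**Conclusion.** The point holds as a defect in the definition of the primary analysis set. Section 13.7.2 states an inclusive rule, and following it can put non-HGG tissue into a 10-versus-10 comparison meant for HGG. The case rests on answering the HGG question without avoidable bias. It does not rest on a power gain.

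The dilution figures are illustrative, because the documents give neither a non-HGG rate nor the drug effect in non-HGG tissue. The firmer numerical statement concerns n: at the implied SD of 0.292, the planned Mann-Whitney test has about 70% to 79% power with 8 to 10 usable per cohort, against the stated 82.5% for 10. It would be an overstatement to say that a single loss destroys the design, since one loss costs about 2 points by the t test. This should be corrected, but it does not invalidate the study.

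**What to change.** In 13.7.2, define the primary analysis set by the same pathology and recording rules in both cohorts: histologically confirmed HGG and a usable ECoG, with usability judged without knowledge of cohort. In Cohort 1 add at least one dose. State that a participant without a usable recording is missing from the primary comparison, and report the number and reason by cohort. Report all participants with an ECoG as a sensitivity analysis. Replace the reference to response with the HFO rate, since evaluability for tumor response is defined separately in 11.1.1.

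The Study Calendar has tissue taken during surgery, and a loading dose 12 to 36 hours earlier cannot plausibly change histology, so the pathology condition adds no treatment-related selection. ECoG usability is determined after dosing, which is why it needs the cohort-blind judgement.

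In 13.1 and 13.2, say up to 20 enrolled, and restate power under the Mann-Whitney test for 8 to 10 usable per cohort with the assumed SD written down.

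The cost is protocol wording and one extra analysis. The downside is a slightly smaller primary set and a less favourable stated power. No clinical procedure changes.

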APPENDIX A PERFORMANCE STATUS CRITERIA

ECOG Performance Status Scale		Karnofsky Performance Scale	
Grade	Descriptions	Percent	Description
0	Normal activity. Fully active, able to carry on all pre-disease performance without restriction.	100	Normal, no complaints, no evidence of disease.
		90	Able to carry on normal activity; minor signs or symptoms of disease.
1	Symptoms, but ambulatory. Restricted in physically strenuous activity, but ambulatory and able to carry out work of a light or sedentary nature (e.g., light housework, office work).	80	Normal activity with effort; some signs or symptoms of disease.
		70	Cares for self, unable to carry on normal activity or to do active work.
2	In bed <50% of the time. Ambulatory and capable of all self-care, but unable to carry out any work activities. Up and about more than 50% of waking hours.	60	Requires occasional assistance, but is able to care for most of his/her needs.
		50	Requires considerable assistance and frequent medical care.
3	In bed >50% of the time. Capable of only limited self-care, confined to bed or chair more than 50% of waking hours.	40	Disabled, requires special care and assistance.
		30	Severely disabled, hospitalization indicated. Death not imminent.
4	100% bedridden. Completely disabled. Cannot carry on any self-care. Totally confined to bed or chair.	20	Very sick, hospitalization indicated. Death not imminent.
		10	Moribund, fatal processes progressing rapidly.
5	Dead.	0	Dead.

NCI Protocol #: N/A
Version Date: 07/27/2020

APPENDIX B MULTI-CENTER GUIDELINES

N/A

APPENDIX D BIOASSAY TEMPLATES

N/A
